**Research on the Association Between the Inclination of the
Proximal Tibiofibular Joint Surface and Medial Compartment
Knee Osteoarthritis**

ClinicalTrials.gov ID: NCT03147495

2017.2.10

Study Protocol

Study Design and Patient Selection

This case-control study (Level III Evidence) will be performed in line with the principles of the Declaration of Helsinki.

The study will be performed to compare the inclination angle of the PTFJ surface in participants with and without medial compartment knee osteoarthritis. A sample size power analysis was conducted before the study, which revealed that a minimum of 39 subjects per group was needed to achieve statistical significance with two-sided $\alpha=0.05$ and $1-\beta=0.80$ and an assumed mean difference between two groups=65% of the standard deviation. The participants will be enrolled at the outpatient clinic of our hospital. The patients with medial compartment knee osteoarthritis will be enrolled at first. The anticipated number of patients is 40, and the female-to-male ratio is expected to be 1:1. Then, the participants of the control group will be enrolled and matched for sex and age (within 5 years) to the patients. The control-to-patient ratio is expected to be 1:1.

Inclusion criteria for participants of the patient group will be: (1) minimum age of 50 years, (2) symptomatic knee osteoarthritis according to the American College of Rheumatology criteria for the classification and reporting of osteoarthritis of the knee joint, (3) predominance of self-reported pain over the medial aspect of the knee, (4) radiographic evidence of medial compartment knee osteoarthritis with an Ahlbäck score of grade I or greater, and (5) radiographic evidence of lateral compartment with Ahlbäck classification grade 0. We will exclude participants with any previous

surgery, severe trauma, inflammatory joint disease, or tumors in the affected limb.

Our controls will be participants aged 50 years or older, without knee osteoarthritis according to the American College of Rheumatology criteria for the classification and reporting of osteoarthritis of the knee joint, and with radiographic evidence of the knee with Ahlbäck classification grade 0. Exclusion criteria will be a history of previous surgery, severe trauma, inflammatory joint disease, or tumors in the affected limb.

All participants should give signed informed consent before enrolment.

Radiographic Examination

Standing anteroposterior knee radiographs and special PTFJ radiographs will be taken for the participants in both groups. The standing anteroposterior knee radiographs will be obtained with the knee extended. The PTFJ radiographs will be acquired with the knee of the participants in approximately 45°-60° of internal rotation. In this projection, the PTFJ articulation can be clearly visible.

Radiographic Evaluations and Measurements

For the standing anteroposterior knee radiographs, radiographic knee osteoarthritis will be evaluated by using the Ahlbäck grading scale, and the femorotibial angle (FTA) will be measured. For the PTFJ radiographs, the degenerative joint disease of the PTFJ will be staged with the Kellgren-Lawrence staging system, and the fibular inclination angle (FIA) and the tibial inclination angle (TIA) of the PTFJ surface to the longitudinal axis of both fibula and tibia will be measured separately. The horizontal type of PTFJ will be defined as the inclination

angle $\leq 20^\circ$, and the oblique type will be defined as the inclination angle $> 20^\circ$.

Radiograph annotations will be deleted. Each participant will be assigned a random and unique number, and participants of the two groups will be mixed. All radiographic evaluations and measurements will be carried out in a blinded, independent, and random fashion by a radiologist, who do not know the study hypothesis, with tools of the digitized picture archiving communication system (PACS, RADinfo Technologies Co.,Ltd, Hangzhou, China). Additionally, 20 participants per group will be randomly selected. The FIA and TIA of the 40participants will be measured again after 1 month by the same radiologist and an orthopedic surgeon who do not know the study hypothesis. The intraobserver reliability and interobserver reliability in the FIA and TIA measurement will be assessed by using an intraclass correlation coefficient (ICC).

Statistical Analysis Plan

Statistical analysis will be performed with SPSS (v25.0; IBM Corp). $P < .05$ will be considered significant. Demographics, laterality of included knees and FTA will be compared between the patient and control groups by using two-sample t test or χ^2 test. Paired-samples t test will be used to compare the difference between the FIA and TIA of all participants.

Any differences of the FIA and TIA between the patient and control groups will

be assessed with the two-sample t test. Furthermore, the participants of each group will be separately grouped into sex subgroups and into two age subgroups. The old age subgroup of each group will include approximately 20 participants with earlier ages, and the remaining participants with higher ages will form the older age subgroups (The number of participants in each subgroup will be as close as possible to 20). The two-sample t tests will be repeated for each sex subgroup and age subgroup in isolation. The odds ratios (ORs) for risk factors of medial compartment knee osteoarthritis will also be calculated by using binary logistic regression analysis.

The PTFJ types will be compared between the two groups by using the χ^2 test. The PTFJ osteoarthritis grades will be compared between the two groups by using the Mann-Whitney U test.

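### Enrolling all patients before any control could turn a drift in how the PTFJ view is obtained into a case-control difference in FIA and TIA

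*Combined protocol and SAP*

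**What the plan says.** Under Study Design and Patient Selection, the order of recruitment is by group: "The patients with medial compartment knee osteoarthritis will be enrolled at first", with 40 anticipated. The plan continues: "Then, the participants of the control group will be enrolled and matched for sex and age (within 5 years) to the patients". Matching is on sex and age, not on date.

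Under Radiographic Examination, both groups receive a standing AP film and a special PTFJ view: "Standing anteroposterior knee radiographs and special PTFJ radiographs will be taken for the participants in both groups". The PTFJ view, from which FIA and TIA are measured, is taken "with the knee of the participants in approximately 45°-60° of internal rotation". The plan gives no date for this view relative to enrolment. It also describes no positioning aid, operator rule or image acceptance check, and no record of the rotation used.

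Under Radiographic Evaluations and Measurements, the safeguards are removal of annotations, random numbering, mixing of the groups ("Each participant will be assigned a random and unique number, and participants of the two groups will be mixed") and blinded reading ("All radiographic evaluations and measurements will be carried out in a blinded, independent, and random fashion by a radiologist"). In the reliability sub-study, 20 participants per group have FIA and TIA "measured again after 1 month by the same radiologist and an orthopedic surgeon who do not know the study hypothesis"; no repeat radiograph is mentioned.

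Under Statistical Analysis Plan, FIA and TIA are compared between groups by a two-sample t test, with no term for date or positioning.

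**The concern.** FIA and TIA are angles measured on a projection, so they depend on how the knee was rotated when the film was taken. If all patient films precede all control films, a change of staff, a learning curve or a shift of habit within the permitted range falls mainly on one group. It adds to, or subtracts from, the true difference.

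None of the planned safeguards reaches this. Mixing and blinding protect the reading of a film, not its acquisition. Re-measuring the same film cannot reveal a positioning difference. The t test takes the shift at face value, and if the groups do not overlap in time, adding calendar date to a model could not separate the two effects without relying on an assumed form for the trend. The question has to be settled in the design. The classification of PTFJ type, with its cut at 20°, uses the same angles and would inherit the same shift.

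**Working it through.** **Inputs from the documents.** Two-sided α = 0.05, power 0.80, difference 0.65 SD, minimum 39 per group, 40 patients anticipated, ratio 1:1 (all from Study Design and Patient Selection).

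**Step 1: the plan's own figure.** For the two-sample t test (noncentral t), the required n at 0.65 SD is 38.14, rounded up to 39. This reproduces the stated minimum. With 40 per group the noncentrality is 0.65 × √(40/2) = 2.907 on 78 degrees of freedom, and power is 81.9%. The sample size is not in dispute.

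**Step 2: effect of a spurious shift.** Let b be an acquisition shift between groups in SD units. This is an assumption, since the documents give no value. With no true difference, the noncentrality is b × √20. With a true difference of 0.65 SD and a shift the other way, it is (0.65 − b) × √20.

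| Assumed b (SD) | False-positive rate | Power if b opposes 0.65 SD |
|---|---|---|
| 0 | 5.0% | 81.9% |
| 0.1 | 7.3% | 68.1% |
| 0.2 | 14.3% | 51.1% |
| 0.3 | 26.3% | 34.0% |

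**Step 3: does the order of recruitment matter?** Assume a linear drift of D in total over 80 consecutive films, so that neighbouring films differ by D/79.

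- Block order (40 patients, then 40 controls): the group means differ by 40 × D/79 = 0.506 D.
- Alternating patient and control: the group means differ by D/79 = 0.013 D.

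For D = 0.4 SD the shifts are 0.20 SD and 0.005 SD. In a simulation of 20,000 replicates, the false-positive rate was about 15% under block order and about 5% under alternation. Over D = 0.2 to 1.0 SD, alternation kept it at about 4% to 5%.

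**Step 4: what shift might rotation produce?** This is illustrative geometry, none of it from the documents: projected angle = arctan(tan φ × cos δ), with true angle φ of 20° to 30°, δ the offset from the best view, and an SD of 6° to 10°. Take a 7.5° change in mean rotation, half the width of the plan's range (60° − 45° = 15°).

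- Smallest effect (φ = 20°, δ from 0° to 7.5°): 20.00° − 19.84° = 0.16°; 0.16/10 = 0.02 SD.
- Largest if δ is at most 15° (φ = 30°, δ from 7.5° to 15°): 29.79° − 29.15° = 0.64°; 0.64/6 = 0.11 SD.
- Largest if δ is at most 30° (φ = 30°, δ from 22.5° to 30°): 28.08° − 26.57° = 1.51°; 1.51/6 = 0.25 SD.

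By the formula in Step 2, shifts of 0.02, 0.11 and 0.25 SD give false-positive rates of about 5.1%, 7.7% and 19.7%.

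**The case against.** The strongest reply is that several links in the chain are not in the plan. It orders enrolment, not imaging. Ahlbäck eligibility makes an early standing AP film likely, but the PTFJ view is a separate film with no date, and both groups could have it later, over the same period. That stands, and the point is therefore conditional.

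A reader might also infer that the knee is positioned by hand, that the range is a declared tolerance, or that radiography staff know which group they are imaging. The plan says none of these. The range may simply mean that rotation is adjusted to each knee until the joint shows clearly. Nor does the plan give any reason to expect drift. Without drift there is no bias, and random variation within the range adds variance rather than a group difference.

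On size, if the best view lies within the plan's range, the offset cannot exceed 15°, and the 7.5° example stays at or below about 0.11 SD. At the low end the effect is negligible. This too stands: the larger figures need stronger assumptions.

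Two replies do not stand. Matching does not require block order, because each control need only follow its own patient, not all 40. Blinded reading of mixed films cannot undo a difference already in the image.

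**Conclusion.** The concern holds as an unaddressed risk, not as a demonstrated bias. The order of enrolment is explicit, the projection is only approximately specified, and every safeguard acts after acquisition. If PTFJ views are taken at or near enrolment and if positioning drifts, the drift is confounded with group and the planned analysis cannot separate it.

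The size is unknown. The error rates and power losses rest on assumed shifts, and the geometry rests on assumed angles, offsets and SD. Under those assumptions, a 7.5° change in mean rotation ranges from about 0.02 SD, which is immaterial, to 0.25 SD, which is not. The stronger reading, that the block order does distort the FIA and TIA comparison, is not supported, because the documents establish neither the imaging order nor any drift. This is a cheap improvement and does not affect the sample size.

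**What to change.** Replace the two sentences on enrolment order with:

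> *Each control will be enrolled and imaged as soon as feasible after the matched patient, so that both groups are recruited and imaged over the same period.*

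This also closes the gap on when the PTFJ view is taken. Use the same positioning instruction for both groups, and record the rotation used for each film so that it can be compared between groups.

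The cost is somewhat more recruitment coordination, one extra field on the imaging form, and a smaller pool of potential controls at any one time for matching on sex and age within 5 years. For that reason no fixed time limit between patient and control is needed. No additional participants, films or readers are required.

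### The 20° rule for PTFJ type conflicts with its stated reference line: 20° or less to the long axis is a surface running along the bone, yet it is labelled horizontal

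*Combined protocol and SAP*

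**What the plan says.** The protocol's section Radiographic Evaluations and Measurements sets up two angles on the PTFJ radiograph, the FIA and "the tibial inclination angle (TIA) of the PTFJ surface to the longitudinal axis of both fibula and tibia will be measured separately". It then gives the type rule: "The horizontal type of PTFJ will be defined as the inclination" angle ≤20°, "and the oblique type will be defined as the inclination angle" >20°. No other line of reference is given there or elsewhere, and the rule does not say which of the two angles it uses.

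The Statistical Analysis Plan uses these measurements in several ways:
- It compares the two angles with each other: "Paired-samples t test will be used to compare the difference between the FIA and TIA of all participants".
- It compares FIA and TIA between patients and controls with two-sample t tests.
- It uses the type variable once: "The PTFJ types will be compared between the two groups by using the χ^2 test".
- It adds a regression, without naming covariates: "The odds ratios (ORs) for risk factors of medial compartment knee osteoarthritis will also be calculated by using binary logistic regression analysis".

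The aim, under Study Design and Patient Selection, concerns the angle rather than the type: "The study will be performed to compare the inclination angle of the PTFJ surface in participants with and without medial compartment knee osteoarthritis".

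**The concern.** A joint surface that makes a small angle with a bone's long axis runs nearly along the bone. A surface lying across the bone makes an angle near 90° with that axis. The rule gives the word *horizontal* to the first and *oblique* to the second, which reverses the ordinary meaning of the label. One of three elements (reference line, number or label) must be a slip, and the documents do not show which.

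Two things are at stake. The first is what the χ² test on PTFJ type compares. The second is direction: in a study about inclination, the reader has to know whether a larger FIA or TIA in patients means a steeper or a flatter joint surface.

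A lesser gap sits in the same sentence. The rule refers to a single inclination angle, although two are measured separately and tested for a difference. A joint whose FIA and TIA fall on opposite sides of 20° has no defined type.

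**Working it through.** **Inputs.** Reference line (long axis of fibula and of tibia), cut-off (20°) and labels come from Radiographic Evaluations and Measurements. The sample-size inputs come from Study Design and Patient Selection: two-sided α 0.05, power 0.80, "an assumed mean difference between two groups=65% of the standard deviation", minimum 39 per group. One assumption is needed: each angle is an unsigned angle from 0° to 90° between two lines on the film, and *horizontal* means lying across the long axis.

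**Step 1: the plan's own figure.** The normal approximation gives n = 2(1.960 + 0.842)² / 0.65² = 2 × 7.85 / 0.4225 ≈ 37.2, so 38 per group. The exact two-sample t calculation gives 38.14, so 39 per group. The stated figure is reproduced. It uses only the difference in SD units, so no reference line enters it.

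**Step 2: geometry.** Angle to the perpendicular = 90° − angle to the long axis.

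| Angle to long axis | Angle to perpendicular | Type as written | Type if ≤20° is taken from the perpendicular |
|---|---|---|---|
| 0° (along the bone) | 90° | horizontal | oblique |
| 20° | 70° | horizontal | oblique |
| 45° | 45° | oblique | oblique |
| 70° | 20° | oblique | horizontal |
| 90° (across the bone) | 0° | oblique | horizontal |

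So *horizontal* at ≤20° fits its label only if the angle is taken from the perpendicular. On the axis scale that is ≥70° (90 − 20), a figure that appears nowhere in the documents.

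**Step 3: consequence for the χ² test.**
- If 20° to the axis is intended, correcting the labels swaps two columns of the 2×2 table. The statistic depends on the squared cross-product difference, so χ² and p do not change.
- If the label is intended but the films are read from the axis as written, the group called horizontal holds the joints at 0°–20° when it should hold those at 70°–90°. Joints strictly between 20° and 70° are oblique either way. Different joints are counted, so the counts and p-value will in general change. By how much depends on the angle distribution, which is not given.

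**Step 4: consequence for the continuous analyses.** Replace each angle x by 90 − x.
- Group means: (90 − m₁) − (90 − m₂) = −(m₁ − m₂). SDs are unchanged, so |t| and the two-sided p are unchanged and only the sign of the difference flips. The same holds for the paired test when both angles are re-referenced.
- Logistic model, if an angle is entered: β(90 − x) = constant − βx, so a per-degree OR becomes its reciprocal.

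**Step 5: which angle sets type.** The paired t test shows that the plan treats FIA and TIA as quantities that may differ. The type rule names neither, and the χ² sentence adds nothing. A joint with the two angles on opposite sides of 20° can therefore be typed either way.

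**The case against.** The strongest reply is that the label shows what was meant. If inclination is read as tilt from the transverse line, 20° or less is horizontal and more is oblique, and all that is missing is a few words naming the zero line. On the other reading, only the names are wrong and the test result is the same. The χ² result is wrong only if the label was intended and the radiologist measured from the axis. In addition, one radiologist, blinded to group, reads the mixed films, so any convention falls equally on patients and controls. The stated aim is met by t tests that do not use the cut-off.

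Most of this stands as a limit on reach. It does not remove the inconsistency. Tilt from the transverse line contradicts the reference line the protocol states; it does not explain it. No other section supplies a perpendicular.

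The unnamed FIA/TIA choice is mainly missing detail, which an analyst could settle by reporting both. It is a minor clarification.

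A reader might go further and infer that the horizontal category would be nearly empty, that the χ² test would have almost no power, or that a sizeable share of joints would change type between FIA and TIA. The documents support none of these. They give no angle mean, SD or FIA–TIA correlation, and any such figure is set by the values one assumes.

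**Conclusion.** The type rule is wrong as written, with limited reach. Reference line, cut-off and label cannot all hold, so the types in the χ² test are either mislabelled (p-value unchanged) or cut at the wrong end (counts and p-value liable to change). The direction of FIA and TIA is unclear to a reader. This rests on the text and on plane geometry, with *horizontal* taken in its ordinary sense.

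Unaffected are the two-sided t tests on continuous FIA and TIA and the 39 per group. Only the sign of an angle difference, and the direction of an OR if an angle enters the logistic model, depends on the reference line.

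Two stronger inferences should be resisted. The first is that the main comparison is invalid or biased between patients and controls: the blinded, mixed reading and the algebra above give no ground for it. The second is that ≥70° to the axis is the correct cut: it follows from the label alone, and the documents do not show that the label is the element to keep.

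**What to change.** Before the films are read, rewrite the type sentence according to what was intended:
- **If the label is intended:** state that the angles are taken from the perpendicular to the long axis and keep ≤20° as horizontal. Equivalently, keep the axis as reference and define horizontal as ≥70°.
- **If 20° to the axis is intended:** keep the reference line and the number, and correct the type labels.

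In the same sentence, say whether FIA, TIA or each separately defines type for the χ² test. In the results, give the reference line beside any signed angle difference and beside any OR for an angle.

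The cost is one or two sentences in the protocol, repeated in the reading instructions. No extra participants, films or readings are needed.

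### The same radiologist grades the knee disease that defines the groups and reads the PTFJ films under one number per participant, so blinding of the PTFJ readings to group is not assured

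*Combined protocol and SAP*

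**What the plan says.** Three parts of the combined protocol and SAP bear on this.

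- **Group definition** (Study Design and Patient Selection). Patients need "radiographic evidence of medial compartment knee osteoarthritis with an Ahlbäck score of grade I or greater". Controls are enrolled "with radiographic evidence of the knee with Ahlbäck classification grade 0".
- **What is read** (Radiographic Evaluations and Measurements). On the AP film, "radiographic knee osteoarthritis will be evaluated by using the Ahlbäck grading scale" and the FTA is measured. On the PTFJ film, "the degenerative joint disease of the PTFJ will be staged with the Kellgren-Lawrence staging system" and FIA and TIA are measured.
- **Who reads, and how** (same section). "All radiographic evaluations and measurements will be carried out in a blinded, independent, and random fashion by a radiologist", who is unaware of the study hypothesis. Annotations are removed from the films, and "Each participant will be assigned a random and unique number, and participants of the two groups will be mixed".

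For 20 participants per group, FIA and TIA are read again a month later by the same radiologist and by an orthopedic surgeon, and reliability is summarised by an ICC. The Statistical Analysis Plan then compares FIA, TIA, PTFJ type and PTFJ grade between the two groups.

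**The concern.** Removing annotations and mixing the groups hides labels. It does not hide disease that is visible on a film the same reader is asked to grade. Grading Ahlbäck means looking directly at the feature that places a participant in one group or the other. If both films reach the radiologist under the same number and the AP film may come first, the radiologist can know a participant's knee disease status when setting the lines for FIA and TIA or staging the PTFJ.

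FIA and TIA are measured by a reader and carry the study's stated comparison. PTFJ type follows from the inclination angle, and PTFJ grade is a judgement. A reading shift that went with visible knee disease would pass straight into the group difference, and no planned analysis would separate it from a true one.

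**Working it through.** **Step 1. Set the statements side by side.**

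| Element | What is stated | What is not stated |
|---|---|---|
| Reader | One radiologist for all first readings | A separate reader for either film type |
| Ahlbäck grade | Part of eligibility: medial I or greater against 0 | That the PTFJ reader is kept from it |
| Code | One random number per participant | A separate code per film |
| Order | Readings made in random fashion | Which film type comes first, or that they are read apart |
| Masking | Blinded; hypothesis unknown to the reader | That blinded means blind to group while PTFJ films are read |

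Among enrolled participants, a reader who agrees with the eligibility grading can tell the groups apart from the Ahlbäck grade. A participant-level number allows the AP film to be linked to the PTFJ film. None of the described steps breaks that link.

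**Step 2. The plan's own scale.** The sample size assumes a difference of 0.65 SD, two-sided 5% and 80% power. The normal approximation, 2 × ((1.960 + 0.842)/0.65)², gives 37.15, rounded up to 38. The exact t calculation gives power 0.799 at 38 and 0.809 at 39 per group. The stated 39 is reproduced.

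**Step 3. Illustration: the main comparison.** The documents give no size or direction for a reading shift, so d below is assumed. The test is the planned two-sample t test with 40 per group, df = 78, no true difference, and noncentrality d × √(40/2) = d × √20.

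| Assumed shift d (SD) | d/0.65 | Rejection rate at nominal 5% |
|---|---|---|
| 0.1 | 15% | 7.3% |
| 0.2 | 31% | 14.3% |
| 0.3 | 46% | 26.3% |

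These shifts are not small against random reading error. With total SD 1 and an assumed ICC of 0.80, 0.90 or 0.95, the error SD is √(1 − ICC). A shift of 0.2 SD is then 45%, 63% or 89% of the error SD, and 0.3 SD is 67%, 95% or 134%. The last row is an extreme case.

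**Step 4. Would the planned ICC show a 0.2 SD shift?**

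- *Intraobserver, shift present on both readings.* A shift s in half the subjects adds s²/4 = 0.01 to the between-subject variance. The ICC becomes (ICC + 0.01)/1.01: 0.802, 0.901 and 0.950 in place of 0.80, 0.90 and 0.95. It does not fall.
- *Interobserver, only the radiologist shifted.* This is a simulation with 20 per group, one reading each and 10,000 runs. The ICC form is assumed to be two-way, absolute agreement, single measure.

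| Assumed ICC | Mean ICC, no shift | Mean ICC, 0.2 SD shift | Fall | Sampling SD |
|---|---|---|---|---|
| 0.80 | 0.793 | 0.784 | 0.009 | 0.061 |
| 0.90 | 0.895 | 0.887 | 0.008 | 0.032 |
| 0.95 | 0.948 | 0.938 | 0.010 | 0.017 |

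Each fall is smaller than its sampling SD, so the planned check would not reveal such a shift. That is a general property of an ICC used for reliability. It means the check cannot stand in for blinding; it is not evidence that a shift exists.

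**The case against.** The plan already commits to blinded, independent and random reading, removes annotations, mixes the groups and uses a reader who does not know the hypothesis. Independent reading may be meant to include reading the two film types apart. If so, what is missing is operational detail and not a safeguard. The route also needs steps that the text does not state: that both films appear under the participant's number, that the AP film is seen first or alongside, and that what is seen there sways the PTFJ reading. A reader who does not know the hypothesis has little reason to shift in a consistent direction.

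Much of this stands. A reader might infer that the reading order is left entirely open. It is not: random fashion does address order, and only the order between AP and PTFJ films is unstated. A reader might also take the one-month repeat as a further gap, because the text says only that the readings are "measured again after 1 month by the same radiologist and an orthopedic surgeon who do not know the study hypothesis", and because PTFJ grade is not repeated. Neither supports this point. The repeats use the PTFJ film alone, so the surgeon has no Ahlbäck task and this route does not reach that reader. The wording on the repeat readers is missing detail, and the lack of a repeat PTFJ grade is a separate reliability matter.

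What does not fall away is the core. Not knowing the hypothesis does not conceal disease status, and the general commitment names no step that keeps the graded AP film apart from the PTFJ reading.

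**Conclusion.** The point holds as a gap in assurance. The steps described do not ensure that FIA, TIA and PTFJ grade are read without knowledge of group. It rests on three things in the text: one radiologist for both film types, Ahlbäck grade as an eligibility criterion that separates the groups, and a code per participant with no stated separation of films.

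A reader might go further and infer that blinding has failed or that the FIA and TIA comparison will be biased. The documents do not support that: they show no sign of a shift and give neither its size nor its direction. The rates of about 7%, 14% and 26% depend wholly on the assumed 0.1, 0.2 and 0.3 SD and should not be cited as the study's error rate. The reason to act is that a procedure needing no extra reader, film or participant would close a route into the main comparison that the planned reliability analysis would not reveal.

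**What to change.** In Radiographic Evaluations and Measurements:

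1. Give AP and PTFJ films separate random codes that cannot be linked by the reader, with the linking key held by someone who takes no part in reading.
2. Have the radiologist read all PTFJ films first, in random order, and lock FIA, TIA and PTFJ grade before opening any AP film for Ahlbäck grade and FTA.
3. Issue new codes for the one-month re-read.

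If separate reading of the two film types is already intended, stating the codes and the order in the plan is enough.

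The cost is a second code list with a held key, and a fixed sequence of reading sessions. One limit remains: the PTFJ film may itself carry visual cues to knee disease, which reading order cannot remove.

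### Must the plan name one PTFJ angle as primary and one as the basis for the 20-degree type?

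*Combined protocol and SAP*

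**What the plan says.** Under Study Design and Patient Selection, the objective is to "compare the inclination angle of the PTFJ surface in participants with and without medial compartment knee osteoarthritis", with the angle in the singular. The sample size of 39 per group covers one two-sided comparison at 0.05 with 80% power and "an assumed mean difference between two groups=65% of the standard deviation". Forty patients and an equal number of controls are planned.

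Under Radiographic Evaluations and Measurements there are two angles: "the fibular inclination angle (FIA) and the tibial inclination angle (TIA) of the PTFJ surface" are measured separately, against the axes of the fibula and tibia. The type rule follows directly. A joint is horizontal at 20° or less, and "the oblique type will be defined as the inclination angle" above 20°. Which angle is meant is not stated.

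The Statistical Analysis Plan applies a single .05 threshold throughout. On the group comparison it reads "Any differences of the FIA and TIA between the patient and control groups will" be assessed by the two-sample t test, so the same test is set for both angles. It also states: "Paired-samples t test will be used to compare the difference between the FIA and TIA of all participants". PTFJ type is compared between groups by a χ² test.

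**The concern.** The objective and the sample size describe one comparison, but the analysis makes two. With no primary angle and no adjustment, a reader could take a significant result on either FIA or TIA as the study's positive finding, and the chance of a false positive would then exceed 5%.

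The type rule looks more serious. The plan does not treat the two angles as interchangeable, because it tests one against the other. A knee with one angle at or below 20° and the other above it receives conflicting types. Two χ² tables therefore fit the written rule, and the plan does not say which is the result. In principle the choice could be made after seeing which table is significant.

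**Working it through.** **Inputs from the documents:** two-sided α 0.05; power 0.80; difference 0.65 SD; 39 per group required; 40 per group planned; 1:1 ratio; type cut at 20°.

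**Assumptions:** the documents give no mean, SD or correlation for FIA and TIA. The correlation ρ is taken as 0.8–0.95 (with 0 as the extreme), the angles as bivariate normal with equal SDs, and the mean as 0 to 1 SD from the cut.

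**1. The plan's sample size.**
Normal approximation: n = 2(z₀.₉₇₅ + z₀.₈₀)²/d² = 2(1.960 + 0.842)²/0.65² = 37.2, rounded up to 38. The exact noncentral-t solution is 38.14, rounded up to 39. The stated 39 is reproduced. Exact power is 80.9% at 39 per group and 81.9% at 40. This holds for FIA and for TIA, each taken as its own question.

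**2. Error rate if either angle alone could make the study positive.**
Rate = 1 − P(|Z₁| ≤ 1.96 and |Z₂| ≤ 1.96), with correlation ρ between Z₁ and Z₂. At ρ = 0 this is 1 − 0.95² = 9.75%.

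| ρ | 0 | 0.8 | 0.9 | 0.95 |
|---|---|---|---|---|
| Rate | 9.75% | 7.8% | 7.0% | 6.5% |

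The excess over 5% is 1.5–2.8 percentage points at ρ = 0.95–0.8. Zero correlation is hard to credit for two angles of one joint surface on one radiograph.

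**3. Knees with conflicting types.**
With equal means lying at the cut, the share is arccos(ρ)/π: 20.5%, 14.4% and 10.1% at ρ = 0.8, 0.9 and 0.95. With means 1 SD from the cut it is 12.2%, 8.6% and 6.1%. The equal-means range is therefore 6.1–20.5%, about 5–16 of 80 knees. If one mean lies a further 0.5 SD from the cut, the range is 9.5–25.3%, about 8–20 of 80.

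**4. What this does to the χ² test** (simulated, 40 per group, no continuity correction).
- No group difference: at least one of the two typings reaches P < .05 in 7.6–9.9% of studies with equal means, against 4.7–5.8% for one named angle.
- Both angles differ by 0.65 SD: one typing is significant and the other is not in 19–32% of studies with equal means (27–36% with the 0.5 SD gap). This is a disagreement about significance, not about direction.
- Much of that disagreement reflects power lost by dichotomising. With equal means, a single named typing reaches P < .05 in only about 39–65% of studies, depending on where the groups lie relative to the cut. The t test on the angle itself does so in 81.9%. Naming an angle would not recover that loss.

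**5. The price of formal adjustment.**
At α = 0.025 per angle, n = 2(2.241 + 0.842)²/0.4225 = 45.0, so 45 per group (47 by exact t). At the planned 40, power falls to 73.2%. Holm gives about 73% if only one angle differs by 0.65 SD, and about 76–80% per angle if both do.

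**The case for a change.** The best argument for a change is the type rule. It leaves an analysis variable undefined, nothing elsewhere in the document settles it, and a sentence or two before the groups are compared would cost nothing. The singular objective also makes the either-angle reading of the t tests possible.

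The textual part of this stands: the plan names no primary angle and no angle for typing. The inference to a necessary change is weaker, for three reasons.

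- **The inflation is conditional.** No section states a success rule, and the document describes a Level III case-control study. Both angles are named in advance and get the same test, so neither is picked from a pool of unplanned outcomes. Two results reported side by side are each valid at 5%.
- **The type rule is incomplete, not unusable.** At or below 20° and above 20° together cover every value of either angle, so each typing can be computed for every knee. Since the two angles are handled in parallel elsewhere, tabulating type by each is a natural reading, and nothing in the plan rules it out.
- **No particular remedy is forced.** The documents give no reason to prefer FIA or TIA. Adjusting two correlated, pre-specified measures in such a study is a matter on which competent statisticians differ, and here it would cost up to about 9 points of power (81.9% to 73.2%).

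**Conclusion.** No change follows. The plan leaves two designations unwritten, and analysts can fill both sensibly: report FIA and TIA as two questions, and either show PTFJ type by each angle or state which angle was used. The 39 per group is right for one comparison, and 40 per group gives each angle about 82% power.

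The either-angle error rate of about 6.5–7.8% rests on assumed correlations of 0.95–0.8 and on a success rule that the plan does not contain. The 6–25% of knees with conflicting types rests entirely on assumed angle distributions. It affects a dichotomised comparison that the study was not sized on, while the angles are also compared directly as continuous measures.

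This conclusion assumes that both t tests are reported and that the basis for typing is disclosed. If only the more favourable angle or table were shown, the false-positive rates above would apply. The plan itself lists both angles, so a missing t test would be visible to a reader.
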